## 5. Statistical Methods

The statistical analyses will be reported using tables, listings, and figures (TLFs). Numbering for TLFs will be based on the recommended numbering convention provided by the International Conference on Harmonization (ICH). Continuous variables will be summarized with means, standard deviations, medians, minimums, and maximums unless mentioned otherwise in this statistical analysis plan (SAP). Categorical variables will be summarized by counts and percentage of subjects in corresponding categories. Footnotes will be used to specify the percent calculation when applicable.

Tables will be summarized for scheduled visits, and individual subject data obtained via the electronic data capture (EDC) system and from external vendors may be presented in listings, as indicated in this SAP. If there are multiple readings taken per visit, the most recent reading from that visit will be used in summaries, unless there are pre-dose and post-dose readings taken at the same visit, as mentioned elsewhere in this SAP.

The analyses described in this plan are considered *a priori*, in that they have been defined prior to database lock. Any analysis added after the database lock will be considered post hoc and exploratory. Post hoc analyses will be labeled as such on the output and identified in the CSR. All analyses and tabulations will be performed using SAS version 9.4 or higher. TLFs will be presented in .pdf format. SDTM datasets will be produced using Version 3.3 of the Implementation Guide. ADaM datasets will be produced using Version 1.0 of the Implementation Guide. Upon completion, all SAS programs used to

produce datasets (SDTM, ADaM) and tables will be validated by an independent programmer. The validation process will be used to confirm that statistically valid methods have been implemented and that all data manipulations and calculations are accurate. Checks will be made to ensure accuracy, consistency with this SAP, consistency within tables, and consistency between tables and corresponding listings.

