8.3.1.2. Repeat Testing

Repeat testing of any clinically significant laboratory test will be performed until the value returns to within the normal range, returns to the baseline level, or clinically stabilizes.

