### **9.2.3. Electrocardiogram**

A standard 12-lead electrocardiogram (ECG) will be performed on Day 1 prior to dosing, Day 8, and Day 56. A summary for change from baseline in the ECG parameters (Ventricular Rate, PR Interval, RR Interval, QRS Interval, QT Interval, QTcB Interval, QTcF Interval) at baseline and all scheduled post-baseline visits will be provided.

The ECG results are to be interpreted as follows: Normal; Abnormal, NCS (not clinically significant); Abnormal, CS (clinically significant). A shift table of the interpretation will

be presented for all scheduled post-baseline visits. Categories for the shift table will be as follows: Missing; Normal; Abnormal, NCS; Abnormal, CS; Total.

Additionally, a categorical summary of maximum post-baseline QTcB Interval ( $> 0$  to  $<= 500$  msec,  $> 500$  msec), maximum post-baseline QTcF Interval ( $> 0$  to  $<= 500$  msec,  $> 500$  msec), and maximum change from baseline ( $> 0$  to  $< 30$  msec,  $>= 30$  to  $<= 60$  msec,  $> 60$  msec) for both QTcB and QTcF will be provided.

A listing of ECG data will also be provided.

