#### **9.2.4. Clinical Laboratory Tests**

Laboratory evaluations (hematology, serum chemistry, coagulation, urinalysis) will be conducted at Screening, Day 1, Day 8, Day 56, and Day 70. Any clinically significant laboratory result after baseline is to be captured as an adverse event and thus included in the summary of adverse events.

Summary statistics for the observed and change from baseline continuous laboratory results will be displayed at baseline and all scheduled post-baseline visits via the following tables:

- Hematology
- Serum Chemistry
- Coagulation
- Urinalysis

For categorical urinalysis results, frequency counts and percentages will be presented.

For laboratory parameters (hematology, serum chemistry, coagulation) where normal ranges are available, shift tables will be presented for all scheduled post-baseline visits. Categories for the shift tables will be Missing, Low, Normal, High, and Total.

A listing for each category of laboratory results shown in the above bulleted list as well as a listing for serology will also be provided, and values will be flagged as Low, Normal, or High relative to normal ranges, if available, and included in the listings. In addition, a listing will be provided for urine drug screen results and a listing will be provided for alcohol breath test screen results.

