#### **9.2.6. Lens Opacities Classification System III (LOCS III)**

An ophthalmic exam including slit-lamp imaging may be performed and would be assessed using LOCS III. Any result that is an AE of Special Interest as defined in Section 5.2 of this SAP is to be recorded.

LOCS III data are collected at Screening, Day 56, Day 70, and Day 112. A summary for change from baseline in four LOCS III parameters (Cortical Lens Opacity, Nuclear Color, Nuclear Opalescence, Posterior Subcapsular Lens Opacity) by eye (OD, OS) at all scheduled post-baseline visits will be provided.

In addition, a shift table for each of the LOCS III parameters by eye will be provided. The possible values for Cortical Lens Opacity (C) range from 0.1 to 5.9, for Nuclear Color (NC) range from 0.1 to 6.9, for Nuclear Opalescence (NO) range from 0.1 to 6.9, and for Posterior Subcapsular Lens Opacity (P) range from 0.1 to 5.9. The exclusion criteria based on LOCS III are as follows:

- C with a LOCS III classification > 2.0 in either eye
- NC with a LOCS III classification > 3.5 in either eye
- NO with a LOCS III classification > 3.0 in either eye
- P with a LOCS III classification > 0.3 in either eye

Given the above exclusion criteria and the definition of AEs of Special Interest as provided in Section 5.2 of this SAP, the categories for the shift tables will be defined as follows, where Nuclear Color will follow the same shift table categorization strategy as Nuclear Opalescence, Cortical Lens Opacity, and Posterior Subcapsular Lens Opacity:

Baseline categorization:

- C: Missing, 0.1 to <= 1.0, > 1.0 to <= 2.0, > 2.0, Total
- NC: Missing, 0.1 to <= 1.5, > 1.5 to <= 2.5, > 2.5 to <= 3.5, > 3.5, Total
- NO: Missing, 0.1 to <= 1.0, > 1.0 to <= 2.0, > 2.0 to <= 3.0, > 3.0, Total
- P: Missing, 0.1 to <= 0.2, > 0.2 to <= 0.3, > 0.3, Total

Post-baseline categorization:

- Change: Missing, <= -0.5, > -0.5 to < 0, No Change, > 0 to < 0.5, >= 0.5, Total

Primary ophthalmic data (assessment of first reading) will be used for summaries, and a listing of primary ophthalmic data will also be provided. Secondary ophthalmic data (secondary readings) will not be summarized or listed.

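### The SAP's last-reading rule, applied literally, means the maximum post-baseline QTc categories need not be true maxima, and it can drop abnormal readings from shift tables if repeats share the visit label

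*SAP*

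**What the plan says.** SAP Section 5 sets two general rules for tables. The first is "Tables will be summarized for scheduled visits". The second covers visits with more than one reading: "the most recent reading from that visit will be used in summaries", "unless there are pre-dose and post-dose readings taken at the same visit". That is the only exception written there.

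One safety measure has its own rule. For LOCS III, SAP 9.2.6 says "Primary ophthalmic data (assessment of first reading) will be used for summaries". The sections on vital signs (9.2.2), ECG (9.2.3) and laboratory tests (9.2.4) say nothing about choosing among readings, so the Section 5 rule reaches them.

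For ECG, SAP 9.2.3 says "A standard 12-lead electrocardiogram (ECG) will be performed on Day 1 prior to dosing, Day 8, and Day 56", which leaves two post-baseline visits. It then plans "a categorical summary of maximum post-baseline QTcB Interval", the same for QTcF, and the maximum change from baseline for both. The cut points are 500 msec for the interval and 30 and 60 msec for the change. It does not say which readings enter the maximum. The ECG interpretation also gets a shift table by scheduled visit.

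For laboratory tests, SAP 9.2.4 says "shift tables will be presented for all scheduled post-baseline visits". Protocol 8.3.1.2 governs repeats: "Repeat testing of any clinically significant laboratory test will be performed until the value returns to within the normal range", or until it returns to baseline or stabilises clinically. Neither document says whether a repeat carries the label of the scheduled visit or is stored as unscheduled.

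**The concern.** A maximum is meant to show the worst value a subject reached. If one reading per visit is selected before the maximum is taken, an earlier and higher reading at the same visit is lost, and so is any reading between scheduled visits. Two programmers could both follow the SAP, one taking the larger of two selected values and the other using all readings, and report different outlier counts. The independent validation in SAP Section 5 checks against the SAP, so it would not settle the difference.

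For laboratory tests, the protocol ties repeats to an abnormal and clinically significant result and continues them until the value settles. If such repeats share the scheduled visit's label, the last-reading rule keeps the value that ended the sequence and drops the one that started it. A normal result triggers no repeat under that rule, so the post-baseline selection runs one way. Safety and tolerability is a primary objective in both documents, and shift tables exist to show out-of-range values whatever the investigator judged.

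**Working it through.** The documents give no figure to reproduce on this point. The check has two parts: what follows from the wording, and an illustration on assumed inputs.

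**1. QTc maximum.** Let A be all post-baseline QTc readings of a subject, and S the readings that survive Section 5: at most one for Day 8 and one for Day 56. S is a subset of A, so max(S) ≤ max(A). Baseline is a single fixed value (SAP 5.2), so the same holds for the maximum change. A first Day 8 reading above 500 msec followed by a same-visit repeat at or below 500 msec would count in the lower category if Day 56 is also at or below 500. With no repeats and no unscheduled ECGs, S = A and nothing is lost.

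**2. By-visit shift tables.** The result depends on how a repeat is stored:

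- Same scheduled visit: the last reading replaces the abnormal one in the table.
- Unscheduled: the scheduled reading stays in the table, and the rule causes no bias there.

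**3. QTc illustration (all inputs assumed).** True change at each of two visits is normal with mean 5 or 10 msec and SD 8, independent between visits. Reading SD is 8 or 12 msec. A reading of ≥30 msec is repeated within the visit with probability r. There are 20 subjects, the upper limit in SAP 6.1, and 400,000 simulated subjects per setting.

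Analytic check at r = 0:

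- Mean 5, reading SD 8: total SD = √(64 + 64) = 11.31; z = (30 − 5)/11.31 = 2.21; upper tail about 0.0136; over two visits 1 − (1 − 0.0136)² ≈ 0.027; × 20 ≈ 0.54 subjects. The simulation gave 0.54.
- Mean 10, reading SD 12: total SD = √(64 + 144) = 14.42; z = 20/14.42 = 1.387; tail about 0.083; 1 − (1 − 0.083)² ≈ 0.159; × 20 ≈ 3.18. The simulation gave 3.18.

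| Same-visit retest rate r | Expected subjects ≥30 msec, all readings | Last reading per visit | Ratio |
|---|---|---|---|
| 0% | 0.54 to 3.18 | 0.54 to 3.18 | 1.00 |
| 25% | 0.54 to 3.18 | 0.42 to 2.57 | 0.79 to 0.81 |
| 50% | 0.54 to 3.16 | 0.31 to 1.93 | 0.57 to 0.62 |
| 100% | 0.54 to 3.18 | 0.08 to 0.64 | 0.14 to 0.22 |

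The losses are therefore about 20% at r = 25% and 78% to 86% at r = 100%. Nothing was computed for the categories above 60 msec or above 500 msec.

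**4. Laboratory illustration (all inputs assumed).** A value is High above 1.96 SD, and q is the probability that a repeat is also High given a High first reading. The share of first-reading Highs kept in the table is 1 − r(1 − q).

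| Test-retest correlation | q | r = 25% | r = 50% | r = 100% |
|---|---|---|---|---|
| 0.5 | 0.183 | 0.80 | 0.59 | 0.18 |
| 0.7 | 0.330 | 0.83 | 0.67 | 0.33 |
| 0.9 | 0.594 | 0.90 | 0.80 | 0.59 |

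For example, at correlation 0.5 and r = 25%: 1 − 0.25 × (1 − 0.183) = 0.796. Here r is the share of all High values repeated within the visit. The protocol requires repeats only of clinically significant results, so r could be low.

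**5. Scale.** With 20 subjects, one reclassified subject moves a percentage by 1/20 = 5 points.

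**The case against.** The strongest reply is that overwriting is not established. Repeating until a value settles, and the at-least-weekly monitoring of Grade 3 or 4 laboratory toxicity in Protocol Table 4, both suggest later dates that may well be stored as unscheduled. The by-visit tables would then keep the original value. This stands, and it is why the shift-table part is conditional. It does not rescue a literal reading of the QTc maximum, because unscheduled readings are also outside the tables.

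Second, the judgement that triggers a laboratory repeat is the same one that sends the result to adverse-event capture under SAP 9.2.4, and listings show the laboratory and ECG data. This largely stands. The limit is Day 70: SAP 9.2.1 excludes events starting after the last dosing day from the treatment-emergent summaries, although the adverse-event listing is not so restricted.

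Third, neither document states replicate ECGs or an ECG repeat rule, and a maximum over the post-baseline period can fairly be read as covering every reading. That makes the QTc part a gap in the wording rather than a demonstrated bias.

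A reader might go further and infer that every summary is biased toward normal. The documents do not support that. LOCS III and paired pre-dose and post-dose readings are outside the rule. Baseline is also a last value (SAP 5.2), so a normal pre-dose retest that replaces an abnormal baseline can add apparent shifts to abnormal.

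**Conclusion.** The point holds as a gap in specification with a known direction for one table. Read literally, Section 5 can only lower the QTc maximum and maximum change, and the SAP does not say otherwise. For the laboratory and ECG shift tables, post-baseline counts move toward normal only if repeats prompted by abnormal results are stored under the scheduled visit. If they are stored as unscheduled, those tables are unaffected.

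The size cannot be obtained from the documents. It turns mainly on the same-visit retest rate, which is not given. A reader might take the high chance that a noisy abnormal value is normal on repeat as the size of the bias. It is not: it is a conditional probability on assumed reliabilities, and it must be multiplied by that unknown rate. The losses above therefore run from zero upward.

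The practical weight is modest: a descriptive study of up to 20 subjects, with adverse-event capture of clinically significant laboratory results and full listings. The choice between first and last reading for by-visit means is closer to preference and is not part of this finding.

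**What to change.** Add to SAP Sections 5 and 9.2.3:

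- Maximum post-baseline QTcB and QTcF, and their maximum changes, are taken over all post-baseline readings, including same-visit repeats and unscheduled ECGs.
- A repeat does not replace the original scheduled reading in by-visit laboratory and ECG shift tables. Alternatively, add one worst-post-baseline row to each shift table that includes repeats and unscheduled values.
- State how a repeat is assigned to a visit: whether it keeps the scheduled label or is stored as unscheduled.

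This takes a few sentences, needs no new data and must be done before database lock. The worst-post-baseline option also needs some added table programming. The downside is that slightly more values will be shown as abnormal. Because baseline stays a single last value, a worst-post-baseline row will show some shifts from measurement noise alone, so it should be labelled as worst-case.

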## **5.1. Handling Missing Data**

For incomplete dates related to adverse events and concomitant medications, the dates will be imputed as follows:

- Incomplete start dates missing day with known month will be imputed as the later of (a) day of first dose started in that month or (b) first of the month.
- Incomplete start dates missing month and day will be imputed as the later of (a) month and day of first dose started in that year or (b) January 1.
- Dates missing year regardless of month or day will be considered as missing.
- An unknown start time with known or imputed date will be imputed with a time of 23:59 for events or medications on Day 1 or as 00:00 on other days.
- An unknown end time with known or imputed date will be imputed the same as a missing start time unless the event or medication is ongoing.
- Events with completely unknown start dates will be considered as treatment-emergent adverse events unless otherwise indicated by a known end date.
- Medications with completely unknown start dates will be considered as concomitant medications unless otherwise indicated by a known end date.
- Any imputed start date or time must come before any known end date or time.
- Missing dates, date parts, and time will be shown as missing in the listings.

For missing values not described in this section of the SAP, imputation will not be performed.

## **5.2. Definitions**

- The baseline measurement for a variable is defined as the most recent non-missing value prior to study treatment.
- The change from baseline measurement for a variable at a post-baseline visit will be derived as the measurement taken at the specified visit minus the baseline measurement.
- Treatment Duration will be derived as the total number of days on treatment as follows: Date of Last Dose – Date of First Dose + 1.

- Study Duration will be defined as the total number of days in the study as follows: Date of Last Visit – Date of Informed Consent + 1.
- Treatment Period is defined to be the period that the subject is active on treatment: Date of First Dose through Date of Last Dose.
- Treatment Compliance over the Treatment Period will be calculated as follows based on drug accountability: Treatment Compliance (%) = Number of capsules taken / Number of capsules expected to be taken  $\times$  100.
- Morning Meal Compliance over the Treatment Period will be calculated as follows based on Day 1 administration and the dosing diary: Morning Meal Compliance is Yes if all responses to the following questions are yes; otherwise, Morning Meal Compliance is No:
  - Was subject dosed at least 1 hour prior to morning meal?
  - Since last visit, has subject been compliant with dosing at least 1 hour prior to the morning meal?
- MADRS responders are defined as subjects who experienced a  $\geq$  50% reduction in MADRS total score compared to baseline.
- MADRS remitters are defined as subjects with a MADRS total score  $\leq$  10.
- CGI-I improvers are defined as subjects who reported “Very much improved” or “Much improved” on the CGI-I scale.
- An adverse event is defined as Related if the event is reported as Definitely Related, Probably Related, or Possibly Related.
- Adverse Events of Special Interest are defined as a change from baseline of  $\geq$  0.5 in Nuclear Opalescence, Cortical Lens Opacity, or Posterior Subcapsular Lens Opacity on the LOCS III scale, or any other ophthalmic results deemed clinically significant by the investigator.
- Age at First MDD Diagnosis will be calculated as follows: Year of the First MDD Diagnosis – Year of Birth, where the Year of the First MDD Diagnosis is defined as the year from the earliest start date of the major depressive episodes determined in Section 7.4 of this SAP.
- Number of Prior MDD Episodes will be calculated as follows: The number of MDD Episodes with a Start Year that is prior to the Year of the Day 1 Visit,

where MDD Episodes are defined as the major depressive episodes determined in Section 7.4 of this SAP.

- Duration of Current MDD Episode will be calculated as follows: Year of the Day 1 Visit – Start Year of the Current MDD Episode, where the Start Year of the Current MDD Episode is defined as the year from the most recent start date prior to the Day 1 Visit of the major depressive episodes determined in Section 7.4 of this SAP.
- Duration from First MDD Diagnosis will be calculated as follows: Year of Day 1 Visit – Year of the First MDD Diagnosis, where the Year of the First MDD Diagnosis is defined as the year from the earliest start date of the major depressive episodes determined in Section 7.4 of this SAP.

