#### **7.4. Baseline Major Depressive Disorder Characteristics**

Major depressive episodes will be determined by using the Medical Dictionary for Regulatory Activities (MedDRA) coded terms of “Depression” and “Major depression” from medical history. The Age at First MDD Diagnosis (years), Number of Prior MDD Episodes, Duration of Current MDD Episode (years), and Duration from First MDD Diagnosis (years) will be calculated as defined in Section 5.2 of this SAP.

A summary will be provided for the Age at First MDD Diagnosis, Number of Prior MDD Episodes, Duration of Current MDD Episode, Duration from First MDD Diagnosis, baseline MADRS total score, and baseline HAM-A total score using the safety population.

A listing of major depressive episodes from medical history with their start and end dates, identified by the aforementioned MedDRA coded terms, and the Age at First MDD Diagnosis, Number of Prior MDD Episodes, Duration of Current MDD Episode, and Duration from First MDD Diagnosis will also be provided.

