## 7.6. Medical History

Medical history verbatim terms captured via the EDC system will be mapped to System Organ Class (SOC) and Preferred Term (PT) using MedDRA version 25.0. Any new, untoward, or worsening medical or psychiatric condition reported after first administration of the investigational product is to be captured as an adverse event.

Medical history events will be summarized by SOC and PT using the safety population. The summary will present the number and percent of subjects having each event. Subjects may have more than one event per SOC and PT. However, a subject is counted once if one or more events at the same level of SOC and PT is reported for the subject. The summary will be displayed in descending order of incidence of SOC and then descending order of PT within SOC.

A listing of medical history events will also be provided.

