## 7.7. Prior and Concomitant Medications

Prior and concomitant medication verbatim terms captured via the EDC system will be mapped to Anatomical Therapeutic Chemical (ATC) classification and preferred name using the World Health Organization Drug (WHODrug) Dictionary Global March 2022 release.

Prior and concomitant medications (defined below) will be summarized separately by WHO ATC classification (using ATC4 and then using the closest available parental ATC classification if ATC4 is not available) and preferred name using the safety population.

- **Prior Medication:** Medications with a start date prior to first dose date will be considered as prior medications regardless of when the medications ended or whether the medications are ongoing.
- **Concomitant Medication:** Prior medications that continue to be taken on or after the first dose date or new medications with a start date on or after first dose date will be considered concomitant medications.

Note that these definitions are not mutually exclusive in that it is possible for a medication to be both prior and concomitant if that medication started prior to first dose and continued after first dose, such as with for example a high blood pressure medication.

These summaries will present the number and percent of subjects using each medication. Subjects may have more than one medication per ATC classification and preferred name. However, a subject is counted once if one or more medications at the same level of ATC classification and preferred name is reported for the subject. Each summary will be displayed in descending order of incidence of ATC classification and then descending order of preferred name within ATC classifications.

A listing of prior and concomitant medications will also be provided. In the listing, each medication will be marked as prior, concomitant, or prior and concomitant.

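### The SAP's count of prior MDD episodes does not exclude the current episode, so a current episode begun in an earlier calendar year is also reported as prior

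*SAP*

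**What the plan says.** SAP Section 7.4 sets the record set: "Major depressive episodes will be determined by using the Medical Dictionary for Regulatory Activities (MedDRA) coded terms of" two kinds, namely Depression and Major depression, among the medical-history records. It applies no filter on whether an episode is ongoing or has ended.

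SAP Section 5.2 then derives three quantities from that one set:

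- Number of Prior MDD Episodes: "The number of MDD Episodes with a Start Year that is prior to the Year of the Day 1 Visit".
- Duration of Current MDD Episode. Its starting point reads: "Start Year of the Current MDD Episode is defined as the year from the most recent start date prior to the Day 1 Visit".
- Duration from First MDD Diagnosis. Its starting point reads: "Year of the First MDD Diagnosis is defined as the year from the earliest start date of the major depressive episodes".

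On reporting, Section 7.4 states: "A summary will be provided for the Age at First MDD Diagnosis, Number of Prior MDD Episodes, Duration of Current MDD Episode" and the remaining baseline items, in the safety population. It also plans "A listing of major depressive episodes from medical history with their start and end dates", shown with the derived values. The protocol does not define the prior-episode count.

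**The concern.** A prior episode would ordinarily mean one that came before the current one. The SAP instead compares calendar years with the year of Day 1 and never subtracts the episode that it has itself labelled current. One record can then supply both the duration of the current episode and a count of one prior episode, so a first-episode subject appears as recurrent in the same table.

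The result also depends on the calendar rather than on the illness. A single episode that began in October gives a count of 0 if Day 1 falls in that December, and 1 if Day 1 falls in the following January.

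At stake is how well one baseline row describes the disease history of a small single-arm cohort. Quality control as planned would not catch it: SAP Section 5 checks programs for consistency with the SAP, so a correct program reproduces the count as defined.

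**Working it through.** The plan states no figure for this variable, so there is none to reproduce. The check applies the written rule to assumed histories and compares it with the number of episodes other than the current one.

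**Is the current episode in the counted set?** Yes. Section 5.2 selects it from the Section 7.4 episodes, and Protocol Table 1 collects both past and concurrent medical history. Nothing in SAP Sections 5.1, 5.2 or 7.4 removes it.

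**Rule as written.** Prior = number of Section 7.4 episodes with start year < Day 1 year.

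**Comparison.** Number of Section 7.4 episodes, other than the current one, that started before the current one.

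| Assumed starts | Day 1 | SAP prior count | Episodes before the current one | Error | Duration of current (SAP, years) | Duration from first diagnosis (SAP, years) |
|---|---|---|---|---|---|---|
| 2021 | 2023 | 1 | 0 | +1 | 2023 - 2021 = 2 | 2023 - 2021 = 2 |
| 2015, 2021 | 2023 | 2 | 1 | +1 | 2023 - 2021 = 2 | 2023 - 2015 = 8 |
| Jan 2023, Jul 2023 | Nov 2023 | 0 | 1 | -1 | 2023 - 2023 = 0 | 2023 - 2023 = 0 |
| Feb 2022 | Jun 2022 | 0 | 0 | 0 | 2022 - 2022 = 0 | 2022 - 2022 = 0 |
| Mar 2015, Feb 2022 | Jun 2022 | 1 | 1 | 0 | 2022 - 2022 = 0 | 2022 - 2015 = 7 |

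The rule is right only when the current episode began in the Day 1 year and every other episode began in an earlier year.

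**When the over-count occurs.** Suppose the current episode began D days before Day 1. Its start lies in an earlier calendar year exactly when Day 1 is among the first D days of its year. An episode longer than 12 months is always over-counted. For shorter ones, in a non-leap year:

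| D (days) | Last Day 1 date affected | Share if Day 1 is spread evenly over the year |
|---|---|---|
| 57 | 26 February | 57/365 = 15.6% |
| 86 | 27 March | 86/365 = 23.6% |
| 182 | 1 July | 182/365 = 49.9% |
| 274 | 1 October | 274/365 = 75.1% |

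The first two rows come from inclusion criterion 6 (at least 8 weeks, or 56 days, before screening) plus a screening period of 1 to 30 days: 56 + 1 = 57 and 56 + 30 = 86. They assume that onset is recorded as exactly 8 weeks before screening; the criterion speaks of diagnosis, not onset. If onset is no later than diagnosis, 57 days is a minimum, and every subject with Day 1 on or before 26 February is over-counted. The 182 and 274 day rows are illustrations. The last column assumes even enrolment; clustered enrolment could put none or all of the subjects inside a window.

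**Effect on the summary row.** Each over-counted subject adds 1/n to the mean. SAP Section 6.1 allows up to 20 subjects, so at n = 20 the shift is 1/20 = 0.05 per subject, and over-counting can raise the mean by anything from 0 to 20/20 = 1.00. With fewer subjects the shift per subject is larger.

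**The case against.** **Prior may simply mean started before Day 1.** Overlap with the current episode would then be intended. The SAP does use the word that way for medications, but there it says so: "Note that these definitions are not mutually exclusive in that it is possible for a medication to be both prior and concomitant". It says nothing similar for episodes. This reading does not rescue the rule either, because a current episode begun earlier in the Day 1 year started before Day 1 and is still left out.

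**The definitions may follow a deliberate year-level convention.** All four MDD history variables work in whole years, and nothing shows that months were recorded. This stands as a constraint on the fix, which must work on years alone. It does not justify leaving the current record in, since one record can be removed whatever the precision of its date.

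**The reach is small and visible.** This stands. SAP Sections 6.2 and 6.4 plan no covariate adjustment and no subgroups, and no efficacy or safety endpoint uses the count. The planned listing shows episode dates beside it, so a reader can check at most about 20 subjects wherever dates were recorded.

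**The under-count is marginal.** This also stands. It needs two separate episodes begun in the Day 1 calendar year, with the current one diagnosed at least 8 weeks before screening.

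**Conclusion.** The definition is wrong as written, and the consequence is minor. It gives +1 whenever the current episode began in a calendar year before Day 1 and, less often, -1 for each true prior episode begun in the Day 1 year. The +1 assumes that the current episode is recorded in medical history under one of the two coded terms. The SAP makes the same assumption when it derives the duration of the current episode.

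Three stronger readings go beyond the documents:

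- A reader might infer that most subjects will be over-counted. The documents give neither episode durations nor an enrolment calendar, so the number affected cannot be derived; the shares above are conditional illustrations.
- A reader might infer that the efficacy or safety results are affected. They are not; the error stays in one descriptive row and one listing column.
- A reader might infer further inflation from one episode entered under both coded terms. No section says that this happens, and duplicate records would be a data-cleaning matter.

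**What to change.** Redefine Number of Prior MDD Episodes in SAP Section 5.2 as the number of Section 7.4 episodes, other than the one identified as the current episode, that started before the current episode. This equals the Section 7.4 episodes starting before Day 1, minus the current one. For the first three histories in the table it gives 0, 1 and 1.

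Add two rules for incomplete dates, since Section 5.1 imputes dates only for adverse events and concomitant medications:

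- **Only years recorded.** Remove the single current record and count the remaining records whose start year is no later than that of the current episode. A medical-history record that gives only the Day 1 year can be taken as starting before Day 1, because under SAP Section 7.6 any new or worsening "condition reported after first administration of the investigational product is to be captured as an adverse event".
- **No start date.** Count the record as prior if its end date precedes the start of the current episode. Otherwise leave it out and footnote it.

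The cost is one revised definition and a short change to its derivation, using data already collected. No other analysis changes.
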